8.9.5 Vital signs

Vital sign parameters (blood pressure, pulse rate, and body temperature) and the scheduled visits and time points (pre-treatment or post-treatment) for assessments are presented in the SoA (see Section 13.6).

Vital sign parameters at each time point and change from baseline to each post-baseline time point will be summarized using descriptive summary statistics for each parameter by treatment group. In addition, weight and BMI reported at Screening, C4 D1, EoT, Safety FU D30 and Safety FU D90 Visit (where applicable) will be summarized in the same way.

The End of Study measurement is defined as last available safety assessment, either at Safety FU D30 or Safety FU D90 Visit (whichever occurs later) or last available safety assessment in case of early trial discontinuation or death. Measurements after switch to cemiplimab monotherapy will not be considered in the derivation of the End of Study measurement.

Vital sign values for each parameter will be assigned an LNH classification according to whether the value is lower (L), within (N), or higher (H) the reference range for that parameter. The values will be summarized using shift tables from baseline to End of Study measurement with respect to reference range values (low, normal, high) for each parameter by treatment group.

Table 8-3: Normal Ranges for Vital Signs

Parameter	Range
Systolic blood pressure	90-140 mmHg
Diastolic blood pressure	40-90 mmHg
Pulse rate	40-100 bpm
Temperature (where applicable)	≤ 38 °C

Scatter plots will be produced for each vital signs parameter comparing baseline and End of Study measurement.

All vital sign data will also be presented in the data listings, abnormal values will be flagged.

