- The patient ICF for trial participation must be signed before any trial-related research procedures or interventions are performed, see Section 10.1.3. Patients who agree to additional optional tumor biopsy sample(s) in case these are taken at the time of disease progression must give written consent for this. Refusal to give consent for the optional tumor biopsy sample(s) does not exclude a patient from participation in the trial.
- Documentation of prostate cancer history and treatments, previous/ongoing concomitant diseases and tetanus vaccination status (see Section 8.3.2).
- [3] A comprehensive physical examination will be performed at screening and abbreviated physical examinations (overall health judgment and change of symptoms) from C1D1 onwards prior to IMP administration, see Section 8.2.1.
- [4] Vital signs (blood pressure, pulse rate, body temperature) should be assessed pre-treatment and 1 h (±15 min), 4 h (±1 h) and 6 h (±1 h) post-treatment and as clinically indicated during C1. Patients must be observed for at least 4 to 6 h after administration of BNT112 and vital signs collected pre-treatment, 4 to 6 h (±1 h) post-treatment and as clinically indicated.
- [5] Only if clinically indicated.
- [6] All prior prostate cancer-related drug treatment will be recorded; other prior medication only for the period of 28 days before the planned IMP administration.
- [7] The period for documentation of concomitant treatment extends from C1D1 until Safety FU-D30 visit. Details of systemic anti-cancer treatments or non-drug anti-cancer therapies (e.g., radiotherapy, surgical therapeutic procedures) started after discontinuation of IMP will be recorded up to the end of the FU period (i.e., up to Efficacy FU-M12).
- Bone scans and CT/MRI of the chest, abdomen, and pelvis will be done at screening, every 8 weeks for the first 24 weeks and every 3 months thereafter (window for tumor assessment is ±7 days of respective visit day). PCWG3 and iRECIST guidelines for imaging will apply. See Section 8.1.1.1.
- [9] Only if routinely performed locally.
- [10] Patients in Part 1 and Part 2 Arm 1A and Arm 1B will be asked if they are willing to provide optional tumor biopsy sample(s) in case these are taken at the time of disease progression.

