Part 1 (dose titration) of the PRO-MERIT trial has been performed in the UK and Hungary and enrollment has been completed with 9 patients dosed. The SRC reviewed the available safety data for patients in Part 1 on 17 MAY 2021. The safety profile observed indicates that BNT112 a tolerable drug product with a manageable safety profile at the defined dose range µg) using the intra-patient step-up dose titration scheme. Observed AEs considered related to the IMP (including pyrexia, flu-like symptoms, hypertension, nausea, chills or headache), are in line with the innate immune activation by RNA-LPX, are transient in nature and manageable by analgesics, antipyretics or fluids at recommended and usual doses. The recommendation was to continue to Part 2 at the selected REDR ( to QCI µg) using the intra-patient step-up dose titration scheme. The annual review of safety data for the IB update occurred on 20 MAY 2021 (data extraction date) and included safety data from patients in Part 1 as well as Part 2. Neither the safety profile nor the benefit-risk assessment were changed.

**Cemiplimab** is given at a dose of mg as an IV infusion over 30 minutes every 3 weeks.

Goserelin acetate is administered at a dose of 10.8 mg as an SC injection into the anterior abdominal wall Q12W, according to the current SmPC (e.g., Zoladex® LA 10.8 mg implant). In order to facilitate interpretation of toxicities with suspected relationship to the IMP, goserelin acetate is to be administered anytime within 7 days prior to the start of BNT112 treatment. In case another ADT is used, it is to be administered in line with the current prescribing information valid in a given country.

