8 STATISTICAL ANALYSES

8.1 General considerations

In general, the statistical analysis will be performed by trial part (i.e., Part 1 and Part 2) and by treatment group in the Part 2 (i.e., Part 1 mCRPC W_pro1, Part 2 mCRPC W_pro1 + Cemiplimab, Part 2 mCRPC W_pro1, Part 2 LPC W_pro1 + Cemiplimab, Part 2 LPC W_pro1). A detailed description of treatment labels to be used for the analysis is provided in Section 13.4.

For Part 2 of the trial all analyses (disposition, baseline characteristics, efficacy and safety (except adverse event (AE) analysis)) will be analyzed by treatment group and in addition for 3 combined treatment groups “Part 2 Total mCRPC”, “Part 2 Total LPC” and “Part 2 Total”. “Part 2 Total” is an optional treatment group only for some predefined tables.

AE analyses will be analyzed for 6 additional combined treatment groups i.e. “Part 2 Total Monotherapy”, “Part 2 Total Combination Therapy”, “Part 2 Total”, “Parts 1 and 2 Total mCRPC”, “Parts 1 and 2 Total Monotherapy” and “Parts 1 and 2 Total”. A detailed description of all combined treatment groups is available in Section 13.4.

Continuous variables will be summarized by treatment group using the following descriptive statistics: number of patients with non-missing data (n), mean, standard deviation, median, minimum, maximum, lower quartile (Q1) and upper quartile (Q3) where appropriate.

Categorical variables will be summarized by treatment group presenting absolute and relative frequencies (n and %) of patients in each category.

Shift tables from baseline will summarize only cases, where both time points are available, to avoid a “missing” category. The percentages are calculated with respect to the available patients.

Generally, only measurements at scheduled visits will be summarized and included in the tables by visit. Unscheduled measurements will be included in the listings, only.

Time-to-event-endpoints (DoR, PFS, and OS) will be analyzed using Kaplan-Meier methodology and censored in accordance with the US FDA Guidance: “Clinical Trial Endpoints for the Approval of Cancer Drugs and Biologics” [6].

The median survival time (including two-sided 95% confidence limits according to Brookmeyer and Crowley) and the first and third quartiles will be presented for each treatment group. Survival rates (including 95% confidence interval (CI) based on Greenwood's formula) as well as the number and percentage of patients with events,

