8.9.4 Laboratory assessments

Clinical laboratory data to be summarized include hematology, blood chemistry, coagulation, thyroid hormones and urinalysis. The clinical laboratory parameters to be assessed are listed in [Table 8-2](#) and the scheduled time points for assessment are presented in the SoA (see Section [13.6](#)).

All laboratory parameters, except serology assessments, are reported in the clinical database using local safety laboratories. Measurements and corresponding Low and High ranges will be converted into Standard International (SI) units. Values outside the normal ranges are classified as “Not clinically significant” or “Clinically significant” by the investigator.

Serology parameters are analyzed by a central laboratory.

For the derivation of the minimum post-baseline measurement / maximum post-baseline measurement / or worst post-baseline toxicity CTC grades, measurements collected at unscheduled visits will be considered.

The End of Study measurement is defined as last available safety assessment, either at Safety FU D30 or Safety FU D90 Visit (whichever occurs later) or last available safety assessment in case of early trial discontinuation or death. Measurements after switch to cemiplimab monotherapy will not be considered in the derivation of the End of Study measurement.

Clinical laboratory parameters at each scheduled visit and change from baseline to each post-baseline time point will be summarized using descriptive summary statistics for each parameter by treatment group.

The number and percentage of patients reporting markedly abnormal clinical laboratory values as reported by the investigator at any point on the trial will be summarized for each parameter by visit and treatment group using the following categories: Clinically significant low, Low, Normal, High, Clinically significant high.

Shift tables from baseline to Minimum Post-baseline / Maximum Post-baseline and to End of Study measurement with respect to reference range values (Clinically significant low, Low, Normal, High, Clinically significant high) will be generated for each parameter by treatment group.

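### SAP 8.9.5 tabulates out-of-range vital signs only as a shift from baseline to End of Study, so no vital-sign table counts patients with transient post-dose excursions

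*SAP*

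**What the plan says.** **Classification and its only table.** SAP 8.9.5 assigns a low, normal or high class using Table 8-3 and adds: "The values will be summarized using shift tables from baseline to End of Study measurement with respect to reference range values". The scatter plots in the same section compare the same two points. The table list in SAP 11.1.1 has three vital-sign outputs: the summary by visit, the shift (14.3.4.2.2) and the scatter plot (14.3.4.2.3). Only the shift table uses the classes.

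**End of Study value.** "The End of Study measurement is defined as last available safety assessment, either at Safety FU D30 or Safety FU D90 Visit", whichever is later, "or last available safety assessment in case of early trial discontinuation or death". For Arm 1B, "Measurements after switch to cemiplimab monotherapy will not be considered in the derivation of the End of Study measurement".

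**What is measured.** Footnote [4] of the Schedule of Activities in Protocol 1.3 says that vital signs "should be assessed pre-treatment and 1 h (±15 min), 4 h (±1 h) and 6 h (±1 h) post-treatment and as clinically indicated during C1". After Cycle 1 it asks for one post-dose set at 4 to 6 h. Footnote [4] in Protocol 1.4 does the same for the LPC arms.

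**Other vital-sign output.** SAP 8.9.5 gives descriptive statistics at each time point and a listing with abnormal values flagged. On unscheduled readings, SAP 8.1 says: "Generally, only measurements at scheduled visits will be summarized and included in the tables by visit"; the rest go to listings.

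**Laboratory comparison.** SAP 8.9.4 provides abnormality counts by visit and shifts to minimum, maximum and End of Study. Unscheduled visits are used "For the derivation of the minimum post-baseline measurement / maximum post-baseline measurement / or worst post-baseline toxicity CTC grades".

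**The concern.** Protocol 4.4 describes the related events seen in Part 1 as "including pyrexia, flu-like symptoms, hypertension, nausea, chills or headache), are in line with the innate immune activation by RNA-LPX, are transient in nature". The post-dose readings fit a reaction that comes and goes within hours. The one table that says who left the normal range looks at a point chosen without regard to dosing, usually weeks after the last dose. A patient whose temperature or blood pressure left the range after several doses and was normal at the safety visit appears there as normal to normal.

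Safety and tolerability is a primary objective in both parts. Clinical significance is judged by the investigator in an open-label trial, so a count against fixed ranges would be a useful objective check on AE reporting. The data for it are collected, but no table makes the count.

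**Working it through.** The plan gives no figure to reproduce. The check is a count from the Schedules of Activities (Protocol 1.3 and 1.4) and a comparison of outputs.

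**Scheduled BNT112 dosing visits through C8D1, all doses given**
- C1: D1, D8, D15 = 3
- C2: D1, D8, D15 = 3
- C3 to C8: D1 of each = 6
- Total: 3 + 3 + 6 = 12

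**Scheduled post-dose vital-sign sets**
- C1: 3 doses × 3 times (1, 4 and 6 h) = 9
- C2 to C8: (12 − 3) doses × 1 time (4 to 6 h) = 9
- Total: 9 + 9 = 18

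An mCRPC patient treated beyond C8 adds one set per cycle.

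**How many of the 18 can enter the shift table**
- Patient who reaches the D30 or D90 visit: 0, because the End of Study value comes from that visit.
- Patient who discontinues early or dies: at most 1 per parameter, because a single last value is used. That value may fall on treatment or less than 30 days after the last dose.
- Arm 1B patient who switches to cemiplimab: again at most 1 per parameter. Protocol 1.3 allows the switch within 28 days after confirmed progression and the EoT visit up to 21 days after the last dose. The last pre-switch value can therefore come from EoT or an earlier visit.

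**Where a post-dose excursion appears**

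| Output | Scheduled post-dose value | Unscheduled value | Counts patients out of range? |
|---|---|---|---|
| Shift, 14.3.4.2.2 | Only if it is the End of Study value | No by-visit role; worst-value use not planned | Yes, at End of Study only |
| Descriptive summary by time point | All 18 | No | No: mean, quartiles and extremes only |
| Listing | All, flagged | All, flagged | No |
| TEAE tables | If recorded as an AE | If recorded as an AE | By AE term |

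The protocol does not say whether extra readings taken as clinically indicated are stored as unscheduled. If they are, they are in listings only.

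**What the AE route leaves out.** Protocol 10.3.3 (abnormal laboratory results and vital signs) does not require every abnormality to be an AE. If the abnormality is a sign of a disease or syndrome, only the diagnosis is recorded. If it causes symptoms without a diagnosis, only the symptoms are. With neither, it is recorded when it changes trial treatment or needs intervention. The uncounted quantity is therefore patients with post-dose values outside Table 8-3 that were judged not clinically significant or were recorded under another term. The documents give no basis for estimating that number.

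**The case against.** The strongest reply is that the primary safety endpoint (SAP 8.9.1) is DLTs and TEAEs, not vital-sign shifts. Clinically significant excursions become AEs and are tabulated in SAP 8.9.3 by preferred term, worst CTCAE grade, relationship and seriousness. The columns cover each arm and pooled monotherapy and combination groups (SAP 13.4). The route works in practice: pyrexia and hypertension in Part 1 were reported as AEs. Protocol 9.4.5 asks only for descriptive statistics of vital signs, which the SAP delivers. SAP 11 calls the table list tentative, and the mock tables, which are a separate document, might contain more. With about 115 patients planned, flagged listings can be read by eye.

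Most of this stands, and it limits the point. Four stronger readings that a reader might infer are not supported:
- *Post-dose reactions are missing from the safety output.* They are missing from the vital-sign abnormality table; the TEAE tables, summaries and listings still carry them.
- *A difference between monotherapy and the combination would be hidden.* The AE tables show both groups side by side.
- *The End of Study value is always at least 30 days after the last dose.* The early-discontinuation and Arm 1B rules allow an earlier value.
- *Hypotension is an observed BNT112 reaction.* The Part 1 events named in Protocol 2.3 and 4.4 include pyrexia and hypertension. Hypotension appears in the DLT criteria (6.6.1.1) and CRS grading (Appendix 8) as foreseen.

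The reply does not explain why laboratory data get minimum and maximum shifts and vital signs do not. Nor does any listed table supply the patient count.

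**Conclusion.** The concern holds as a limited reporting gap. The low/normal/high class is tabulated at a time that misses transient post-dose excursions: 0 of 18 scheduled post-dose sets through C8D1 for a patient who reaches the safety visit. The SAP already uses a better method for laboratory data. Neither the primary safety endpoint nor any protocol commitment is compromised, so this is an inexpensive improvement to the safety description.

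The count of 18 assumes that all 12 doses are given on schedule. The conclusion also assumes that the mock tables add no vital-sign abnormality count beyond SAP 11.1.1.

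**What to change.** In SAP 8.9.5 and Table 14.3.4.2.2:

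1. Add shifts from baseline to the minimum and to the maximum post-baseline value for each parameter, using all scheduled post-dose and unscheduled values, as SAP 8.9.4 does for laboratory data. For temperature only the maximum is informative, since Table 8-3 sets no lower limit.
2. State that in Arm 1B only values before the cemiplimab switch are used, in line with the existing End of Study rule.
3. Optionally, add the number and percentage of patients, by cycle and treatment group, with a post-dose value newly outside Table 8-3 relative to that day's pre-dose value. The comparison with pre-dose is needed. Table 8-3 puts the upper limits at 140 and 90 mmHg, while exclusion criterion 1d applies only from 160 or 100 mmHg. A plain count would include eligible patients who are above range before every dose.
4. Keep the End of Study shift.

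The cost is SAP wording and one extended table from data already collected. One caution for reading it: a worst value becomes more likely to be out of range as readings accumulate, so it should be read alongside exposure. The optional count by cycle helps with that. No dose, schedule or clinical rule changes.

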8.9.6 ECG

ECGs parameters and the scheduled visits for assessment are presented in the SoA (see Section 13.6).

ECGs will be judged by the investigator as normal, abnormal not clinically significant (NCS) or abnormal clinically significant (CS). The number and percentage of patients with clinically significant ECG findings will be summarized by treatment group for visit.

Ventricular heart rate (bpm) at each visit and change from baseline to each post-baseline time point will be summarized using descriptive summary statistics by treatment group.

All ECG parameters will also be presented in the data listings.

8.9.7 Physical examination

Comprehensive physical examinations will be performed at screening. During the treatment, the investigators should make an overall health judgement and make only in-depth examinations if clinically indicated.

Depending on timing (before or after signing the ICF for trial participation), the clinically significant findings of the physical examination have to be recorded as medical/surgical history or as AEs.

The complete physical examination at screening including the following body systems: General Appearance, Head and Neck, Skin, Eyes, Ears, Nose & Throat, Lungs, Heart, Abdomen, Lymph Nodes, Musculoskeletal System (including Extremities and Spine), Neurological Findings, Genito-Urinary System, Anus/Rectum, and Other.

At all visits after screening, an abbreviated physical examination will be performed.

The abbreviated physical examination includes an overall health judgement (any new or worsened abnormalities since previous assessment [Y/N]) and brief interim history (change of symptoms). In-depth physical examinations are required if obvious pathological signs are visible or in the case the patient states any signs or symptoms.

The number and percentage of patients with assessments of normal, abnormal NCS, abnormal CS at screening visit will be displayed in a summary table for each body system. For visits after Screening, the number of percentages of patients with any new or worsened abnormalities since previous assessment will be presented. Details regarding the new or worsened abnormalities will be reported in the physical examination listing.

All physical examination data will be listed.

8.9.8 ECOG PS

ECOG PS will be assessed according to the SoA (see Section 13.6).

The following ECOG PS categories will be reported:

GRADE	ECOG PERFORMANCE STATUS
0	Fully active, able to carry on all pre-disease performance without restriction
1	Restricted in physically strenuous activity but ambulatory and able to carry out work of a light or sedentary nature, e.g., light house work, office work
2	Ambulatory and capable of all selfcare but unable to carry out any work activities; up and about more than 50% of waking hours
3	Capable of only limited selfcare; confined to bed or chair more than 50% of waking hours
4	Completely disabled; cannot carry on any selfcare; totally confined to bed or chair

GRADE	ECOG PERFORMANCE STATUS
--------------	--------------------------------

5	Dead
---	------

Available from: <https://ecog-acrin.org/resources/ecog-performance-status>

The number and percentage of patients in each ECOG PS category will be summarized by visit and treatment group.

Shift tables from baseline to the D1 post baseline visits for each cycle with respect to ECOG PS categories by treatment group will be generated. All ECOG PS data will be listed.

9 QUALITY CONTROL

SAS programs are developed to produce output such as analysis data sets, summary tables, data listings, figures or statistical analyses. An overview of the development of programs is detailed in Syneos Health Developing Statistical Programs SOP (3907).

Syneos Health Developing Statistical Programs SOP (3907), Conducting the Transfer of Biostatistical Deliverables SOP (3908) and the SAS Programming and Validation Plan (version 2.0, dated 23 APR 2021) describes the quality control procedures that are performed for all SAS programs and output. Quality control (QC) is defined here as the operational techniques and activities undertaken to verify that the SAS programs produce the output by checking for their logic, efficiency and commenting and by review of the produced output.

10 PROGRAMMING CONSIDERATIONS

All tables, data listings, figures, and statistical analyses will be generated using SAS® for Windows, Release 9.4 or higher (SAS® Institute Inc., Cary, NC, USA). Computer-generated table, listing, and figure output will adhere to the following specifications.

10.1 General Considerations

- A separate SAS program will be created for each output.
- Each output will be stored in a separate file.
- Output files will be delivered in rtf format. In addition, 3 combined pdf files for tables, figures and listings will be delivered (combined pdf file including bookmarks).
- Numbering of TFLs will follow ICH E3 guidance.

